APPENDIX C – RECRUITMENT LOG

	Date	Age	Gender	Race	Care Needs	Relationship to PWD	Rural?	Agreed to participate?	Reason for not enrolling (if provided)	Study ID (if agreed)
1			F / M		A lot / Some / A little		Y / N	Y / N		
2			F / M		A lot / Some / A little		Y / N	Y / N		
3			F / M		A lot / Some / A little		Y / N	Y / N		
4			F / M		A lot / Some / A little		Y / N	Y / N		
5			F / M		A lot / Some / A little		Y / N	Y / N		
6			F / M		A lot / Some / A little		Y / N	Y / N		
7			F / M		A lot / Some / A little		Y / N	Y / N		
8			F / M		A lot / Some / A little		Y / N	Y / N		
9			F / M		A lot / Some / A little		Y / N	Y / N		
10			F / M		A lot / Some / A little		Y / N	Y / N		
11			F / M		A lot / Some / A little		Y / N	Y / N		
12			F / M		A lot / Some / A little		Y / N	Y / N		
13			F / M		A lot / Some / A little		Y / N	Y / N		

APPENDIX G – ADVERSE EVENT FORM

Adverse Event Form

STUDY NAME

Site Number: _____

Pt ID: _____

Has the participant had any Adverse Events during this study? Yes No (If yes, please list all Adverse Events below)

Severity	Study Intervention Relationship	Action Taken Regarding Study Intervention	Outcome of AE	Expected	Serious
1 = Mild 2 = Moderate 3 = Severe	1 = Definitely related 2 = Possibly related 3 = Not related	1 = None 2 = Discontinued permanently 3 = Discontinued temporarily 4 = Reduced Dose 5 = Increased Dose 6 = Delayed Dose	1 = Resolved, No Sequel 2 = AE still present- no treatment 3 = AE still present-being treated 4 = Residual effects present-not treated 5 = Residual effects present- treated 6 = Death 7 = Unknown	1 = Yes 2 = No	1 = Yes 2 = No (If yes, complete SAE form)

Adverse Event	Start Date	Stop Date	Severity	Relationship to Study Treatment	Action Taken	Outcome of AE	Expected?	Serious Adverse Event?	Initials
1.									
2.									
3.									

Adverse Event

Form Version 1.0

APPENDIX H – SERIOUS ADVERSE EVENT FORM

National Center for
Complementary and
Integrative Health

Serious Adverse Event (SAE) Report Form

STUDY NAME

Protocol Number: _____

Site Name: _____

Pt ID: _____

Date Participant Reported:

— d — / — m — m — / — y — y — y —

1. SAE onset date: — d — / — m — m — / — y — y — y —

2. SAE stop date: — d — / — m — m — / — y — y — y —

3. Location of SAE: _____

4. Was this an unexpected adverse event? Yes No

5. Brief description of participants with no personal identifiers:

Sex: F M Age: _____

Diagnosis for study participation: _____

6. Brief description of the nature of the SAE (attach description if more space is needed):

7. Category of the SAE:

Date of death — / — / —
(dd/mmm/yyyy)

Congenital anomaly/birth defect
 Required intervention to prevent permanent
impairment

Life threatening

Other: _____

Hospitalization – initial or prolonged

Disability/incapacity

8. Intervention type:

- Medication or nutritional supplement (specify): _____
- Device (specify): _____
- Surgery (specify): _____
- Behavioral/lifestyle (specify): _____

APPENDIX J – ADVERSE EVENTS/SERIOUS ADVERSE EVENTS LISTING

Data as of: _____

Date of report: _____

Participant ID	Onset Date	Stop Date	Expected (Y/N)	Relationship to Intervention* (Y/N)	Outcome**	Description of SAE

* *Definite, Possible, Not Related*

** *Outcome:*

Recovered, without treatment

Recovered, with treatment

Still Present, no treatment

Still Present, being treated

Residual effect(s) present – no treatment

Residual effect(s) present- being treated

Subject died

APPENDIX K – BUILDING A BRIDGE PROTOCOL DEVIATIONS LOG

Building a Bridge Protocol Deviations

Deviation Date	Description	Action Taken	AE or SAE form filled out	Reporting Plan

Deviation Date	Description	Action Taken	AE or SAE form filled out	Reporting Plan

Deviation Date	Description	Action Taken	AE or SAE form filled out	Reporting Plan

APPENDIX M – UNIVERSITY OF IOWA HAWK IRB REPORTABLE EVENT QUESTIONS (FROM ONLINE FORM)

1. What type of event are you reporting?

- A serious adverse drug event (either expected or unexpected) occurring in a subject enrolled by a UI investigator/research team member.
- A serious adverse device effect (either anticipated or unanticipated) occurring in any subject enrolled either by the UI investigator/research team member or enrolled by a non-UI investigator at another site.
- Receipt of new information that may impact the willingness of subjects to participate or continue participation in the research study.
- An unanticipated problem involving risks to subjects or others which occurs in a subject enrolled by a UI investigator/research team member or that would impact subjects or conduct of the study at UI.
- Noncompliance with federal regulations or the requirements or determinations of the IRB.

2. Reportable Event Form ID/Short Description:

- Date of occurrence:
- Describe the unanticipated problem:

V. Unanticipated Problem

3. Did this unanticipated problem occur in a subject enrolled by a UI investigator/research team member?

Yes No

V. Unanticipated Problem

4. Did this unanticipated problem affect others associated with the subject or others associated with the research at UI (e.g. research team, family members of research subjects)?

Yes No

V. Unanticipated Problem

5. How many subjects have signed a UI consent to enroll in this study?

6. Is this study permanently closed to enrollment at UI?

Yes No

7. In the judgement of the UI Principal Investigator, how likely is it that this unanticipated problem was related to the study drug or procedures associated with this protocol?

- Definitely Related
- Probably Related / Likely
- Possibly Related / Maybe
- Probably Not Related / Unlikely
- Definitely Not Related

If you have any attachments that you want to include with your Reportable Event Form (such as supporting documentation), include them here.

APPENDIX N – PARTICIPANT INCENTIVE FORM

Name: _____

Do you have U.S. Citizenship: Yes No

Mailing Address:

Amount paid or value of the item given as compensation: \$20.00

If you Circled 'No' for 'Do you have U.S. Citizenship' please also provide the following:

Immigration (visa) status:

Tax residency country (may not be the same as citizenship country)
Permanent foreign address:

U.S. address: _____

APPENDIX R – PARTICIPANT ID LIST

Participant ID List

APPENDIX S – PHONE CALL LOG

Phone Call Log

APPENDIX U – POTENTIAL PARTICIPANT CONTACT INFORMATION FORM

Name: _____

Do you give permission for Manager [name] to contact you about the Building a Bridge Research Study? [name] will make up to 3 attempts to contact you: Yes No

Phone Number:

E-mail Address:

Preferred Method of Contact: Phone E-mail

APPENDIX V – INTERVIEW SCRIPTS (WITH ADVERSE EVENT SAFETY CHECK)

Interviewer Script 1: Baseline Scheduling and Basic Information

Interviewer first contact with Caregiver by phone:

Hi this is _____ at the University of Iowa College of Public Health. I am calling because you expressed interest in receiving more information about the Building a Bridge project when you were at the _____ clinic.

If Caregiver wants more information:

The purpose of this study is to understand the impact of dementia diagnoses on individuals and those providing support. We have developed a program to help people providing support to someone with dementia and are testing to see how it helps those involved. If you enroll in this study, there is a 50% chance that you will participate in the program and a 50% chance that you will receive the usual care provided by the clinic. All participants, whether they receive the program or not, will complete three surveys either in person or over the phone with me. The surveys take between 30 and 50 minutes to complete. If you would like to participate, we can schedule the first one today. The other two will happen in 3 months and in 6 months. I also want to let you know that even if you receive the usual care during this study, you will have the opportunity to receive the program we created after you complete the 6 months survey. Participants need to be 18 years or older, living in Iowa, and must be caring for someone who has been diagnosed with Alzheimer's or dementia within the past 6 months.

Are you interested in participating in this study?

If yes

Great! The first step is to do a survey, which I will call the baseline survey. It takes about 40-50 minutes to complete. Would you like to schedule a time for me to either come to you or call you to do the survey?

Make sure to note the time, location, best phone number to reach participant, ask about internet (if doing online), ask if participant wants a reminder call, and let them know that it might be helpful to have their packet.

If no

Ok, no problem. For our record, may I ask why you decided not to participate?

Research Assistant Script 2: Baseline Survey

Interviewer calls to do baseline

Hi this is _____ at the University of Iowa College of Public Health. I am calling/here to do the baseline survey for the Building a Bridge project with _____.

Before we get started, I just wanted to go through a few things about study

Read through consent letter

Thank you for participating in our study. We would like to ask you some questions about your experiences supporting individuals diagnosed with dementia, how you are feeling in general, about clinical or community-based services that are available, as well as some background information about you and the person who received dementia diagnosis who we refer to as “the individual” in this survey. I’m going to start with questions about your background.

Conduct Baseline Interview

After Baseline:

Thank you for taking the time to speak with me today and answer these questions. I will be sending you \$20.00 in the mail and providing a follow up call to make sure you received the money.

If participant decided not to participate:

That's ok. For our records may I ask you why you decided not to participate?

Research Assistant Script 3: 3 Month Follow-up Survey

Interviewer calls to do 3 month follow-up

Hi this is _____ at the University of Iowa College of Public Health. I am calling/here to do to do the 3 month follow-up survey for the Building a Bridge project with _____.

Before we get started, I just wanted to check and see how you are doing. Have you noticed anything different since you started the study? *If any adverse events, create an AE form and fill out.*

Thank you for participating in our study. We would like to ask you some questions about your experiences supporting individuals diagnosed with dementia, how you are feeling in general, about clinical or community-based services that are available, as well as some background information about you and the person who received dementia diagnosis who we refer to as “the individual” in this survey. I’m going to start with questions about your background.

Conduct 3 month follow-up survey

After Interview:

Thank you for taking the time to speak with me today and answer these questions. I will be sending you \$20.00 in the mail and providing a follow up call to make sure you received the money.

If participant decided not to participate:

That's ok. For our records may I ask you why you decided not to participate?

Research Assistant Script 4: 6 Month Follow-up Survey

Interviewer calls to do 6 month follow-up

Hi this is _____ at the University of Iowa College of Public Health. I am calling/here to do to do the 6 month follow-up survey for the Building a Bridge project with _____.

Before we get started, I just wanted to check and see how you are doing. Have you noticed anything different since you started the study? *If any adverse events, create an AE form and fill out.*

Thank you for participating in our study. We would like to ask you some questions about your experiences supporting individuals diagnosed with dementia, how you are feeling in general, about clinical or community-based services that are available, as well as some background information about you and the person who received dementia diagnosis who we refer to as “the individual” in this survey. I’m going to start with questions about your background.

Conduct 6 month follow-up survey

After Interview:

Thank you for taking the time to speak with me today and answer these questions. I will be sending you \$20.00 in the mail and providing a follow up call to make sure you received the money.

Thank you for participating in this study. Your participation is now complete. You can contact me at _____ if you have any further questions. You will receive your \$20 reimbursement and a letter that will let you know how you can find the results of this study and who to contact with further questions.

If participant decided not to participate:

That's ok. For our records may I ask you why you decided not to participate?

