The intervention consists of two parts, Options Counseling (OC) and Health Education (HE). The OC part includes family assessment, counseling and provision of emotional support, access assistance, and development of independent-living plans (care plans) using the Iowa's Heritage Area Agency on Aging database. The Options Counselor is trained to use motivational interviewing techniques to develop family care plans, provide emotional support, and connect families to available services and programs in the community. The HE part includes post-diagnosis family education using the 7-module health education toolkit developed specifically for this study based on the literature and expert reviews. OC-HE will conduct initial assessment to determine educational needs within 2 weeks of participant's randomization into the intervention group and develop initial care plan; and will conduct 5 monthly follow-up calls to adjust the care plan and provide educational components appropriate at each point. This intervention aims to create direct links between the medical clinics, home and community-based services (HCBS), and family.

Participants assigned to the usual care control group will participate in baseline, as well as 3- and 6-months

follow-up surveys. Those in usual care group will receive a general informational brochure from the Alzheimer's Association, and will be given an option of receiving a call from their local Options Counselor after completing the 6-month survey.

Study duration is about 18 months. We aim to start participant enrollment in August, 2019, complete recruitment by September, 2020, and complete data collection by March 2021. Each participant will be enrolled in this study for about 6 months from enrollment to final interview.

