6.0 Informed Consent

Documents Provided Prior to Consent

- Flyer (*Appendix D*)
- Study Information Sheet (*Appendix E*)
- Consent Letter (*Appendix F*)

Consent Procedures and Documentation

About the study: To collect the information about the reach of our program, the research and clinical team will collect information about all potential participants' age, gender, race, physical disability status (collected by whether the person needs assistance with evacuation), rurality, whether the potential participant agreed to participate, and the reason for declining. The PWD who receives the Alzheimer's or related dementia diagnosis is not the participant in the study, but the PWD is welcome to be in the room while the study is discussed. The research team member will explain that the study consists of a baseline interview, randomization into intervention group or standard care group, completing the intervention (if randomized into the intervention group), and a 3 month, and 6 month interview. Those in the standard care group will complete the baseline, 3 month, and 6 month interview on the same schedule as the intervention group, and will have an option of receiving a call from an options counselor after the 6 month interview has been completed. This call from an options counselor is not the intervention being tested, but standard care participants will be connected to an options counselor who will do their own options counseling after the research is complete if the participants desire. The purpose of this protocol is to make sure that anyone who agrees to participate in this study has access to support regardless of their study group status.

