anticipate our initial visits to take about 2 hours. After the home visit, the Options Counselor will call the participants each month for the next five months to implement follow up phone intervention sessions that will last between 30 to 60 minutes. As a rough guideline, we anticipate one to two modules to be delivered during the initial visit and one module to be delivered at each of the five follow-up phone encounters. We will provide all modules to the participants at the end of the intervention as a resource. At the end of the 6-month study intervention period, participants will have every Educational Module offered in this intervention. At the end of the study the participants will also have access to the local Area Agency on Aging to continue receiving resources, counseling and options. Through this intervention participants will not have intentional interaction with other caregivers or families that are also participating in this study.

Participants in the control group will complete baseline and 3-month and 6-month follow-up interviews. They will receive a standard information brochure from the Alzheimer's Association as part of the usual care provided at the partnering clinics. After completing the 6-month follow-up interview, these participants will have an option of receiving a phone call from an Options Counselor at their local Area Agency on Aging or receiving a contact information of their local OC if they wish to initiate the call.

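### Recruitment Script 1 offers usual-care participants the tested programme after 6 months, while sections 2.0, 6.0 and 7.0 offer them only an optional options-counselor contact

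*Protocol*

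**What the plan says.** Script 1 in Protocol Appendix V introduces a single programme: "We have developed a program to help people providing support to someone with dementia and are testing to see how it helps those involved". It states the odds: "there is a 50% chance that you will participate in the program and a 50% chance that you will receive the usual care". It then tells the caller that, even under usual care, "you will have the opportunity to receive the program we created after you complete the 6 months survey". After one sentence on eligibility, the caller is asked whether they are interested in participating.

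Three sections of the Protocol describe what usual-care participants are offered:

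- Section 2.0: they "will be given an option of receiving a call from their local Options Counselor after completing the 6-month survey".
- Section 6.0: an optional options-counselor call after the 6-month interview. "This call from an options counselor is not the intervention being tested". The counselor "will do their own options counseling after the research is complete if the participants desire".
- Section 7.0: after the 6-month interview, "these participants will have an option of receiving a phone call from an Options Counselor at their local Area Agency on Aging", or contact details if they prefer to make the call themselves.

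The SAP describes no offer to usual-care participants.

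**The concern.** Script 1 is an operative document: an interviewer reads it to people deciding whether to accept an even chance of usual care. What they will get if allocated to usual care bears directly on that decision. If the script offers something the plan does not provide, the statement is inaccurate whether or not any bias follows.

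There is also a possible effect on the comparison. Caregiver burden is a primary outcome (section 1.0), and use and knowledge of home and community-based services are surveyed (section 5.0). A control who expects the study programme at month 6 has some reason to put off seeking help, including options counseling, which Appendix A describes as an existing service of the Area Agency on Aging. If that happened, usual care could look worse than it would otherwise be.

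**Working it through.** The point rests on no power, sample-size or alpha figure, so the check is a comparison of texts.

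**1. Which programme does the script mean?** Script 1 mentions only one: the one the team developed, is testing, and allocates with 50% probability. By section 2.0 that is OC-HE, made up of Options Counseling and Health Education. The sentence on usual care can only refer to this.

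**2. What are controls offered?**

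| Source | Offer after 6 months | Tested programme? |
|---|---|---|
| Appendix V, Script 1 | The programme the team created | Yes, by step 1 |
| Section 2.0 | Optional call, local options counselor | Not offered |
| Section 6.0 | Optional call; the counselor's own counseling | Expressly not |
| Section 7.0 | Optional call, or contact details | Not offered |

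The three sections agree with each other. The script is the outlier.

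**3. Is the difference one of substance?** Yes. Section 2.0 says the Health Education toolkit was developed for this study, while options counseling is an existing service (Appendix A). The part the team created is the part no section offers to controls. Section 7.0 does say that all modules are handed over at the end of the intervention, but that passage describes the intervention arm. The control group has its own paragraph, which mentions no modules.

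**4. Does a later script make good the offer?** No. Script 4, at 6 months, closes by saying participation is complete and mentions the payment and a results letter. It refers neither to the programme nor to the counselor call.

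**5. Who hears the sentence?** Script 1 is for first contact by phone, and the paragraph is read if the caregiver wants more information. Section 6.0 also describes explanation, screening and consent in the clinic. The documents do not give the split between routes. The number of controls who heard the sentence therefore lies between 0 and the planned 53.

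**6. Can an effect on outcomes be sized?** No. The documents give no figure for service use among controls, for any delay in seeking services, or for the relation of either to burden.

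**The case against.** The strongest case on the other side has four parts.

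- **Enrolment does not happen on Script 1.** It only schedules the baseline survey. Under section 5.1 a caregiver is enrolled after the consent letter has been read through and they agree, and Script 2 repeats that step. This stands. The letter and the information sheet are not in the review copy, so a reader who infers that participants were still misinformed when they consented goes further than the documents allow. Section 6.0 has staff explain the later call, but does not clearly say that participants are told it is not the tested intervention. A later correction would in any case leave the recruitment script wrong.
- **Not every control hears it.** This stands, for the reason in step 5. A reader might take all 53 controls to be affected; the documents support that only as an upper bound.
- **The delayed offer is in the plan anyway.** This also stands. Sections 2.0, 6.0 and 7.0 all place the offer after the 6-month assessment, and section 6.0 gives a reason: access to support whatever the allocation. Any incentive to wait, or to complete the survey first, would exist under the right wording too. What the script can add is a more attractive offer.
- **Bias is not shown.** A reader might conclude that the usual-care comparison is distorted and the benefit inflated. Nothing in the documents says that controls delayed seeking help, and no section restricts their use of services. Service use is surveyed in all participants at baseline, 3 and 6 months, so a difference could be seen, though not its cause. An added reason to stay for the 6-month survey could also help retention.

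It can also be said that an opportunity is softer than a promise. That is fair, but the plan does not provide the opportunity either.

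**Conclusion.** The contradiction is certain: on what usual-care participants may receive after 6 months, Script 1 disagrees with three sections of the Protocol, and one of them expressly says the later call is not the tested intervention. Caregivers recruited by phone who ask for more information are given an inaccurate description at the point of recruitment. That is sufficient reason to correct it.

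The effect on the comparison is a plausible inference with no size attached. It assumes that some controls heard the sentence, that it was not corrected before baseline, and that it led them to delay seeking services beyond any delay the planned offer would cause. None of these can be verified from the documents. The case for change is accurate information and removal of an avoidable inducement to wait, not a demonstrated bias.

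**What to change.** Replace the Script 1 sentence with the content of sections 6.0 and 7.0: after the 6-month survey, usual-care participants may choose a call from their local options counselor, or that person's contact details, and this is not the programme being tested. Check the consent letter and study information sheet against the same statement. Optionally, add that usual-care participants remain free to use community services during the study; this would be new text, as the sections cited do not contain it.

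Section 2.0 planned to finish recruitment in September 2020 and the SAP is dated January 2022, so enrolment may already have closed. In that case, document what controls were told, by which recruitment route, and what they were offered afterwards, and report this when interpreting the usual-care comparison.

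The cost is a one-sentence change, a minor IRB modification and a slightly less attractive recruitment message. The analysis is unaffected.
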